6.11. Electroencephalograms

6.11.1. Screening and Baseline Procedures and Assessments

Sleep deprived EEG's shall be conducted during screening and shall be utilized for excluding patients at increased seizure risk, predicting overall seizure risk, informing dose escalation decisions once dosing has commenced, and contributing to the overall safety monitoring program. These EEGs shall also be used as a baseline to facilitate detection of changes in future EEGs completed throughout the study. Screening EEG's should be conducted only after all other Screening activities have completed. Subjects previously consented or screened for KTX-101 who have undertaken a previous sleep-deprived EEG within the last 12 months, will not have to have this procedure repeated.

Subjects will be admitted to the clinic at Day -3 to undertake a sleep deprived EEG on Day -2. Subjects will be requested to maintain their usual sleep routine, however, only sleep for 4 hours (\pm 1 hour) prior to undertaking the 1-hour screening EEG. The EEG recording will be reviewed to identify any IEDs or electrographic seizures. If present, the subject will be excluded and be discharged from the unit. Volunteers that display this increased risk are referred to an epilepsy clinic for specialist follow-up.

During the study, 24-hour continuous EEG recordings will also be reviewed as a safety assessment for any IED's pre and postdose (as a marker of increased susceptibility postdose).

EEG data will form part of the CRC data review package from each cohort (including sentinels and rest of cohort dosing) to mitigate seizure potential and allow safe dose escalation. The presence of epileptiform discharges observed on the EEG recordings will also contribute to the stopping rules criteria and, if present, no further dose escalation will occur.

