5.3.4. Dose Escalation

An evaluable subject is one that has been dosed, completed all assessments, and had their data reviewed by the CRC.

Blinded data to be reviewed by the CRC for each subject will include (as a minimum): PK (up to 30 hours postdose for Part A and 24 hours postdose for Part B), EEG, ECG, vital signs, pulse oximetry, neurological examination, and any adverse events.

The CRC may approve dose escalation following review of cohort data if:

- No drug related SAE's occurring within 48 hours of administration of KNX100 or placebo is observed in any subject in the dose group under evaluation.
- No drug related AE's of Grade 3 or greater are observed in 2 or more subjects within a dose group.
- The mean KNX100 C_{max} **OR** AUC does not exceed 84.9 ng/mL or 82.7 ng×h/mL respectively **and** the mean KNX100A C_{max} **OR** AUC does not exceed 26.5 ng/mL and 45.7 hr × ng/mL, respectively, the exposure associated with 1/10th of the NOEL of 2.75 mg/kg observed in the 14-day dog EEG study.
- No emergence or evidence of other PI-deemed and or medical monitor-deemed clinically significant abnormal vital signs, neurological and physical examination, or safety parameters postdose have been observed.

Dose increases will be permitted once review of data from all evaluable subjects has been performed.

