6.17.6. Suspected Adverse Reaction

Suspected adverse reaction (SAR) means any AE for which there is a reasonable possibility that the drug caused the AE; that is, there is evidence to suggest a causal relationship between the drug and the AE. This definition is taken from US FDA regulation (21 CFR 312.32(a)) but is also consistent with the Australian NHMRC (2016) guidance *Safety Monitoring and Reporting in Clinical Trials Involving Therapeutic Goods*. Emergence of IED's recorded following dose administration will be considered an SAR.

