6.20. Study Stopping Rules

CTCAE, version V5, 27Nov2017 criteria will be used during this study (Refer also to [Section 6.17.3](#)).

The study will be discontinued for any of the following:

- Using CTCAE criteria, the study will be stopped for review if drug-related toxicities of Grade 3 or greater (or a SAE) are observed in 2 or more subjects on active treatment in that dose group.
- If any unacceptable safety findings are identified at any time during the study and/or if ≥ 1 subject experience a related SAE or a related significant AE that, in the opinion of the CRC, warrants discontinuation of the study.
- Any other safety concern based on the judgment of the PI and/or medical monitor and reviewed by the CRC.

If post dosing EEG's demonstrate evidence of epileptiform abnormalities, in any subject as evaluated by an epileptologist or a Level 3 ANZAN certified neurologist, all dosing will be suspended pending review and approval by the CRC.

The decision to stop the study will be made by the CRC. Refer to [Section 9.8](#) for additional information on the CRC.

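### The protocol gives no single consequence for epileptiform discharges on EEG: sections 5.3.4 and 6.20 could allow an escalation that section 6.11.1 forbids

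*Protocol*

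**What the plan says.** Four places in the protocol bear on what happens to escalation after an epileptiform discharge.

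- **Section 6.11.1** (EEG procedures): discharges seen on the recordings feed into the stopping rules. The same sentence then attaches a consequence of its own: "if present, no further dose escalation will occur".
- **Section 6.20** (stopping rules): "If post dosing EEG's demonstrate evidence of epileptiform abnormalities, in any subject", as read by an epileptologist or certified neurologist, "all dosing will be suspended pending review and approval by the CRC".
- **Section 5.3.4** (dose escalation): "The CRC may approve dose escalation following review of cohort data if" four listed conditions hold. None mentions EEG. EEG is, however, in the minimum data that the CRC must review, and the last condition requires that no "clinically significant abnormal vital signs, neurological and physical examination, or safety parameters postdose have been observed", as deemed by the investigator or medical monitor.
- **Section 9.8.1** (blinded data review): for Part B, clinically significant EEG findings are among the items whose frequency and severity decide whether escalation is acceptable. SAP section 3.4 repeats this list and adds no rule.

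Two further provisions concern the event but not escalation. Section 6.17.6 states: "Emergence of IED's recorded following dose administration will be considered an SAR". Section 6.21.1 makes emergent, expert-read discharges a criterion for discontinuing the individual subject.

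**The concern.** Section 3.2.1 makes CNS effects the main basis for choosing the starting and escalating doses, and section 6.17.5 names EEG observation as one of the mitigations for seizure risk. A discharge after dosing is therefore the finding for which the escalation rule most needs to be unambiguous.

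As written, the answer depends on which section the CRC opens. Section 6.11.1 is a flat bar. Section 6.20 is a suspension that the CRC can lift. Section 5.3.4, where a reader would look for the escalation rule, leaves the matter to clinical judgement. No passage sets an order of precedence.

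The cost runs both ways. On one reading, escalation could proceed after a finding that the protocol elsewhere says ends it. On the other, a single background discharge unrelated to drug, possibly in a placebo subject, would end escalation.

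**Working it through.** The plan states no figure on this point, so the main check is a comparison of the rules. The arithmetic at the end is illustrative.

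**Triggers and consequences side by side**

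| | Trigger | Reader | Consequence |
|---|---|---|---|
| 6.11.1 | Discharges on the EEG recordings; the paragraph before covers on-study recordings before and after dosing | Not stated | No further escalation, no exception |
| 6.20 | Abnormality on a post-dose EEG, any subject | Epileptologist or certified neurologist | All dosing suspended until CRC approval; scope of approval not stated |
| 5.3.4 | EEG not named; general safety-parameter condition | Investigator or medical monitor | Escalation blocked only if deemed clinically significant |
| 9.8.1 (Part B) | Clinically significant EEG findings | CRC review | Weighed in the escalation decision |

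**One event followed through the rules**

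Take one expert-read discharge after dosing, in one subject, that is not serious and is not deemed clinically significant. Suppose mean exposure is below the caps.

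1. Section 6.17.6: it is a suspected adverse reaction. No severity grade is assigned.
2. Section 6.21.1: that subject meets a discontinuation criterion.
3. Section 6.20: all dosing is suspended. Suppose the CRC reviews the case and approves resumption.
4. Section 5.3.4, condition by condition:
   - no related serious event within 48 hours: satisfied;
   - "No drug related AE's of Grade 3 or greater are observed in 2 or more subjects within a dose group": satisfied, since only one subject is affected;
   - exposure caps: satisfied by supposition;
   - no clinically significant safety finding: satisfied by supposition.

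   The CRC may approve escalation.
5. Section 6.11.1: escalation may not occur.

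Steps 4 and 5 disagree about the same event, and nothing in the protocol or SAP resolves it.

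**Treatment arm**

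The Grade 3 stopping rule in 6.20 is limited to subjects on active treatment. The EEG rule in the same section covers any subject, and 6.11.1 is silent on arm. As written, a discharge on placebo has the same effect as one on KNX100.

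**Illustration of how often the rule might be invoked without a drug effect**

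Inputs: seven named cohorts (four in Part A, three in Part B) of 8 subjects, 6 active and 2 placebo (section 3.1). That gives 7 × 8 = 56 subjects, of whom 7 × 2 = 14 are on placebo. The planned total of about 64 leaves room for added cohorts, which are not counted here. The per-subject chance p of a background discharge being recorded on study is an assumption, because the documents give none.

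Formula: P(at least one) = 1 − (1 − p)^n.

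| p (assumed) | n = 14, placebo | n = 56, all |
|---|---|---|
| 0.5% | 1 − 0.995^14 = 6.8% | 1 − 0.995^56 = 24.5% |
| 1% | 1 − 0.99^14 = 13.1% | 1 − 0.99^56 = 43.0% |
| 2% | 1 − 0.98^14 = 24.6% | 1 − 0.98^56 = 67.7% |

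**The case against.** The strongest reply is that the two explicit rules govern different actions. Section 6.11.1 restricts escalation and 6.20 restricts all dosing. Both can be obeyed: suspend, and if the CRC allows dosing to resume, do not escalate. Section 6.11.1 itself points to the stopping rules, and the wording of 5.3.4 is permissive, so it need not override a bar stated elsewhere. This is a fair reading and it stands as a possible one. It is not written anywhere, though. The stopping rules to which 6.11.1 refers do not contain the no-escalation consequence, and 5.3.4 does not carry it either.

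A reader might infer three contradictory outcomes. The text does not support that. There are two stated consequences, which are compatible on one reading, and a set of escalation conditions that reaches EEG only by judgement.

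A reader might also infer that exposure could simply carry on after a true signal. That is too strong as well. All dosing is suspended first, the affected subject meets a discontinuation criterion, and section 9.8 requires a neurologist with EEG expertise on the CRC.

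On timing, discharges at screening exclude the subject, so they cannot be the trigger. Only the on-study predose segment is unclear. On treatment arm, the wording may be a deliberate blinded safety choice. Section 5.6 already lets the code be broken if the CRC needs it, and section 3.2 allows specific CRC members to be unblinded. The open question is what is meant, not whether a new unblinding procedure is needed.

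The probabilities need the same caution. Subjects are screened by sleep-deprived EEG and for seizure and family history, so the true rate may lie outside the assumed range. The 56-subject figure does not measure the chance that a placebo discharge ends escalation; the 14-subject figure is the relevant one. An event in the last named cohort would block no planned step. Leaving that cohort out gives 12 placebo subjects (5.8%, 11.4%, 21.5%) and 48 in all (21%, 38%, 62%).

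Finally, the CRC Plan cited in 9.8 is not among the documents and might set precedence. The protocol would still need to agree with it.

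**Conclusion.** The inconsistency is real and is one of wording. Section 6.11.1 forbids further escalation if discharges are present. Sections 5.3.4 and 6.20, followed as written, can permit it after a single non-serious discharge that is not deemed clinically significant. The triggers also differ: 6.20 requires a post-dose, expert-read finding, and 6.11.1 states neither condition.

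This conclusion rests on the text alone and needs no event rate. The size is illustrative only. If background discharges occur in 0.5% to 2% of subjects, at least one would be expected among the placebo subjects with a chance of about 7% to 25%, and among all 56 subjects with a chance of about 24% to 68%. The rule could therefore plausibly be called on even if the drug had no effect on EEG.

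Because the finding is the trial's main safety signal, the sections should be reconciled before the CRC has to apply them. This review takes no position on which consequence is right.

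**What to change.** Reconcile protocol sections 5.3.4, 6.11.1, 6.20 and 9.8.1 so that they state:

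1. one trigger, including whether on-study predose recordings count and who must read them;
2. one consequence for escalation, and whether CRC approval under 6.20 can include escalation;
3. whether the reference in 6.20 to any subject is meant to include placebo subjects, consistent with the existing unblinding provisions in 5.6.

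Enter the result as an explicit EEG criterion in 5.3.4 and cross-refer to it from the other three sections. Bring SAP section 3.4 and the CRC Plan into line. The choice of clinical rule belongs to the sponsor.

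The cost is a protocol wording amendment with matching edits to those two documents. No new data, procedures or subjects are needed.

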6.11.2. Dosing Phase Assessments

During the SAD phase, subjects will undertake a continuous ambulatory EEG from at least 30 minutes predose to 24 hours (± 1 hour) after administration of their dose.

Please refer to the SOA in [Appendix 1](#), [Appendix 2](#), and [Appendix 3](#) for details regarding timing for assessments in the MAD phase.

6.12. Pharmacokinetic Assessments

Venous blood samples for determination of concentrations of KNX100 and its metabolites in plasma will be collected at the times presented in [Appendix 3](#).

6.12.1. Determination of Drug Concentration in Pharmacokinetic Samples

Samples for determination of plasma concentrations of KNX100 and its metabolites will be analyzed using an appropriate bioanalytical method. Full details of the analytical method will be described in a separate bioanalytical report. All samples that are within the known stability of the analytes of interest (i.e., KNX100 and its metabolites) at the time of receipt by the bioanalytical laboratory will be analyzed. In addition, the PK samples may be subjected to further analyses by the Sponsor to further investigate the presence and/or identity of additional drug metabolites.

Drug concentration and exposure will be monitored in individual subjects and will form the basis of dose escalation decisions and study stopping criteria as defined in [Section 6.20.1](#).

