5.3.1. Sentinel Subject Review and Toxicity Management

Part A Cohorts 1 through 4 will initiate dosing with 2 sentinel subjects who are randomly assigned so that 1 subject receives KNX100 and the other receives placebo. Following dosing of study medication, site personnel will observe the sentinel subjects for 48 hours, at which time the investigator will review the safety and tolerability for both sentinel subjects. This will include housing of the sentinel subjects in the Phase 1 unit for 30 hours postdose and then a follow up phone call at approximately 48 hours postdose administration.

Data reviewed will include AEs, clinical laboratory results, vital signs, and ECGs, EEGs, and PK parameters for both subjects. PK will be evaluated to ensure that exposure has not exceeded the maximum clinical exposure cap defined in [Section 6.20.1](#). Upon acceptance of reviewed data by the site and CRC, dosing may continue for the remaining 6 subjects. The investigator will document the review and decision by email to Sponsor representatives.

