6.20.1. Maximum Clinical Exposure

Clinical PK will be considered as criteria for escalation of clinical doses. Dosing will not exceed $1/10^{\text{th}}$ of the exposure associated with the NOEL of 2.75 mg/kg observed in the 14-day dog EEG study (KNX100 C_{max} and $AUC_{0-\text{last}}$ of 84.9 ng/mL and 82.7 hr \times ng/mL, respectively and KNX100A C_{max} and $AUC_{0-\text{last}}$ of 26.5 ng/mL and 45.7 hr \times ng/mL, respectively).

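### The exposure cap is tested on the cohort mean in protocol 5.3.4, tied to individual subjects in 6.12.1 and given no statistic in 3.2.2 and 6.20.1, and nothing says what follows when mean and individual results differ

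*Protocol*

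**What the plan says.** Five sections of the protocol state, or point to, the same four limits: KNX100 Cmax 84.9 ng/mL and AUC 82.7 h×ng/mL, and KNX100A Cmax 26.5 ng/mL and AUC 45.7 h×ng/mL. They are set at one-tenth of the exposure at the no-effect dose in the 14-day dog EEG study.

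- **5.3.4 (escalation):** the CRC may approve escalation if, among other conditions, "The mean KNX100 C_{max} OR AUC does not exceed 84.9 ng/mL or 82.7 ng×h/mL respectively". The two metabolite limits are tested in the same way. The unit is the cohort mean.
- **6.12.1 (PK samples):** "Drug concentration and exposure will be monitored in individual subjects and will form the basis of dose escalation decisions and study stopping criteria", with a reference to 6.20.1. The unit monitored is the subject.
- **6.20.1 (maximum exposure):** "Clinical PK will be considered as criteria for escalation of clinical doses. Dosing will not exceed" the limits. No statistic is named.
- **3.2.2 (maximum dose):** escalation stops if Cmax or AUC passes the limits or looks likely to. The CRC may then stop the study or lower later doses. No statistic is named.
- **5.3.1 (sentinels, Part A only):** "PK will be evaluated to ensure that exposure has not exceeded the maximum clinical exposure cap defined in" 6.20.1. The pair is "randomly assigned so that 1 subject receives KNX100 and the other receives placebo", so the check rests in effect on one active subject. It governs release of the other six subjects in that cohort.

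SAP 3.4 says that the CRC reviews PK data and does not name the statistic. Neither document covers the case of a subject above the cap with the mean below it.

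**The concern.** The cap is a main control on seizure risk in a first-in-human study. Section 3.2.1 argues for at least a 10-fold margin on CNS effects, and 6.17.5 names monitoring of maximum plasma exposure as a mitigation. A limit on a mean and a limit on each subject are different safeguards: if the mean sits at the cap and exposure varies at all, some subjects are above it.

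As written, one set of cohort data can satisfy 5.3.4 and still contain exposures that a reader of 6.12.1 with 6.20.1 would call above the cap. The sentinel step does not close the gap. It sees one active subject per Part A cohort, and 5.3.1 provides no such step for Part B.

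**Working it through.** **1. The plan's own exposure figure.** Section 3.2.1 uses dose = CL/F × AUC with CL/F 356,000 mL/h and AUC 23.3 h×ng/mL. 356,000 × 23.3 = 8,294,800 ng = 8.29 mg, which matches the stated 8.3 mg. The documents give no exceedance figure to reproduce.

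**2. Where planned doses sit.** Mean AUC = dose / CL/F, assuming linear kinetics.
- 25 mg (Table 3, Cohort 3): 25,000,000 / 356,000 = 70.2 h×ng/mL, and 70.2 / 82.7 = 85% of the cap.
- 30 mg (Table 4, Cohort 2): 30,000,000 / 356,000 = 84.3 h×ng/mL, or 102% of the cap.

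Dose / CL/F gives AUC to infinity, while 6.20.1 states the cap on AUC to the last quantifiable concentration, so these percentages are approximate. They place planned doses in the range where the choice of statistic matters.

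**3. An example that needs no distribution.** Six active AUCs of 100, 95, 90, 75, 70 and 64 sum to 494, with mean 82.3. That meets the 82.7 criterion in 5.3.4, and three of the six are above 82.7.

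**4. How often this happens.** Inputs: 6 active subjects per cohort (3.1) and log-normal exposure with s² = ln(1 + CV²). The CV is an assumption, taken as 20% to 60%. Cohorts of six were simulated (300,000 per setting), each was rescaled so that its arithmetic mean equalled a chosen fraction of the cap, and subjects above the cap were counted.

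| CV | Mean = cap: expected number above, of 6 | Mean at 90%: two or more above | Mean at 80%: two or more above | Mean at 70%: two or more above |
|---|---|---|---|---|
| 20% | 2.83 | 51% | 4% | <1% |
| 30% | 2.75 | 70% | 20% | 2% |
| 40% | 2.67 | 77% | 36% | 7% |
| 50% | 2.60 | 80% | 46% | 14% |
| 60% | 2.54 | 81% | 53% | 21% |

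With the mean equal to the cap, exactly two or three subjects are above it in 81% to 84% of cohorts. With the mean at 80% of the cap, at least one is above it in 50% (CV 20%) to 98% (CV 60%).

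**5. The highest subject.** With the mean equal to the cap, the highest of six has a median of 1.25 (CV 20%) to 1.74 (CV 60%) times the cap, and a 95th percentile of about 1.5 to 2.6 times. The margin to the dog no-effect exposure for that subject is 10 / 1.25 = 8.0 to 10 / 1.74 = 5.7 at the median, and 10 / 2.6 = 3.8 at the extreme.

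**6. How far the two readings diverge.** If the true mean equals the cap, P(subject above) = 1 − Φ(s/2), which is 0.461 at CV 20% and 0.391 at CV 60%. All six are at or below the cap with probability 0.539⁶ = 2.5% to 0.609⁶ = 5.1%. The mean criterion is met in 52% to 55% of the same cohorts. For an even chance that all six are below the cap, the true mean would have to be about 80% (CV 20%) to 59% (CV 60%) of it, or about 66 to 49 h×ng/mL for AUC.

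**The case against.** A reader might infer that the protocol sets a per-subject test in 5.3.1 and 6.12.1 that 5.3.4 contradicts outright. The text does not go that far. Section 6.12.1 says where the data come from and what they inform. A cohort mean is also built from individual monitoring, and 6.20.1, to which it points, names no unit. Section 5.3.1 is individual only because one sentinel is on active drug. Only 5.3.4 names a statistic, and the wording of 6.20.1 can be read as describing a dose level. The subject withdrawal criteria in 6.21.1 contain no exposure criterion, which fits that reading.

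A reader might also infer that a sentinel above the cap stops the cohort while a later subject with the same value passes. Section 5.3.1 leaves continuation to site and CRC acceptance, and 3.2.2 gives the CRC a choice of actions. Section 5.3.4 permits escalation without requiring it.

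Other safeguards do not depend on the mean. Under 5.3.4 the CRC sees PK for each subject. Under 6.20, epileptiform findings in any subject suspend dosing pending CRC review. A CRC Plan, not among these documents, may define the unit.

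All of this stands, and it limits the claim. It does not settle which statistic the cap applies to. A limit worded as absolute still has one reading under which a cohort passes and another under which it does not.

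**Conclusion.** The point holds as an unreconciled safety threshold. It is more than missing detail, because following 5.3.4 as written permits escalation with individual subjects above the limit in 6.20.1.

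The size depends on how close the mean is to the cap. Two or three of six above it is typical only when the mean is at or just below the cap. At 80% of the cap the count is usually none to two, and at 70% two or more is uncommon. A reader might infer from the near-cap figures that the safety margin is lost; on these figures it narrows to about 6- to 8-fold for the median highest subject, and to about 4-fold at the extreme.

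The frequencies rest on the log-normal form and the assumed CV range. Placing the 25 and 30 mg doses near the cap rests on linear kinetics and the protocol's CL/F. The textual conflict and the six-subject example rest on neither.

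**What to change.** Reconcile 3.2.2, 5.3.1, 5.3.4, 6.12.1 and 6.20.1 so that each states which statistic the cap applies to, for sentinel release, escalation and stopping, and what follows when individual and mean results differ. If a mean is kept anywhere, say whether it is arithmetic or geometric and that it is taken over active subjects only. With two placebo zeros included, an eight-subject mean of 82.7 would correspond to an active mean of 82.7 × 8 / 6 = 110.3 h×ng/mL.

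Have the CRC PK output report the chosen statistic and the number of subjects above the cap, in a form that keeps the blind. Align the CRC Plan with the result. Which rule to adopt is for the sponsor and CRC.

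The cost is a wording amendment and one more line in the CRC output. No new data are needed.
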